3.4 Harms

[figure not shown]
The number and percentage of patients experiencing treatment-related serious adverse events and fracture-related complications will be presented by treatment arm (**Table 13**). No formal statistical testing will be undertaken.

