2.0 TRIAL POPULATION

2.1 Patient Flow through the Trial

The number of patients screened, included, and excluded will be presented in a flow diagram (**Figure 1**). The figure will include the number of participants who were randomly assigned to the two treatment groups. It will also include the number of participants who were subsequently deemed ineligible by the Central Adjudication Committee.

We will summarize the number of patients excluded by reason (**Table 1**) and the number of participants deemed ineligible by the Central Adjudication Committee by reason (**Table 2**). Participants deemed ineligible by the Central Adjudication Committee will not be included in any analysis, as per guidance from Fergusson et al.³

Figure 1 will include participant follow-up and the number of participants who were lost to follow-up, along with the reason, over the course of the trial.

2.2 Participant Demographics, Injury, and Fracture Characteristics, and Surgical and Perioperative Care Details

We will use descriptive measures to summarize participant demographics, baseline information, injury, fracture characteristics, surgical, and perioperative care details of the sample stratified by treatment group (**Tables 3 and 4**). We will use means and standard deviations (SDs) or medians and interquartile ranges (IQR) for continuous data, and categorical data will be presented as frequencies and percentages. We will examine key baseline differences between those who stopped the CBT program early and those who did not. We will not statistically test for differences

in these characteristics between treatment groups (**Section 3.2**). The potential clinical importance of any imbalance between treatment groups will be noted.

Additional details on the trial population have been published previously.²

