3.0 ANALYSIS

3.1 Analysis Methods

The primary and secondary analyses will be conducted following intention-to-treat (ITT) principles, ensuring that participants are analyzed in their originally assigned treatment groups, regardless of adherence or protocol deviations. The date on which the participant's fracture(s) occurred will be used as the starting point for all time-to-event analyses.

We will use multiple imputations to account for missing data in the analyses and minimize potential bias under the assumption that the data are missing at random (MAR). This approach will allow for the uncertainty associated with missing values to be properly accounted for, improving the robustness of statistical inferences.⁴ Additionally, as we anticipate high rates of early withdrawal, we will account for this in the analyses, if needed.

If any of the analysis models fail to converge, we will remove adjustment covariates one by one until convergence is achieved. The same set of covariates will be used consistently across all models in the primary and secondary analyses.

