4.0 FIGURES AND TABLES

Figure 1: Consort Flow Chart for Trial Participants

*Please refer to Table 1 for reasons for exclusion

**Please refer to Table 2 for reasons for ineligibility per the Central Adjudication Committee

***Participants were assessed at follow-up regardless of number of sessions completed

Table 1: Reasons for Exclusion*

Reasons for Exclusion	Total n (%) (n= XX patients excluded)
Patient does not have an eligible fracture	
Patient has a concomitant injury which, in the opinion of the attending surgeon, is likely to impair function for as long as or longer than the patient's extremity fracture(s)	
Patient is facing current or impending incarceration	
Currently not experiencing any pain in the fracture region despite being fully weight bearing	
Patient has active psychosis	
Patient has active suicidality	
Patient has an active substance use disorder that, in the judgement of the treating surgeon, would interfere in the patient's ability to partake in the CBT and/or the study	
Patient does not have the cognitive ability and language skills to participate in CBT	
Patient is already participating in or planning to start other psychological treatments (including CBT) within the duration of the study (12 months)	
Patient does not have consistent online access from a smartphone/internet-enabled device with a minimum operating system able to use the CBT provider's application	
Anticipated problems, in the judgement of study personnel, with the patient participating in CBT intervention and/or returning for follow-up	
Patient is not willing to participate in CBT	
Currently enrolled in a study that does not permit co-enrolment in other trials	
Previously enrolled in the COPE trial	
Patient was not screened/approached within 2-12 weeks following their fracture	
Patient's fracture was not treated operatively with internal fixation	
Patient did not provide informed consent	

*This table shows all response options for the data collected. In the primary manuscript, some data categories may be removed if there are no responses selected.

Table 2: Reasons for Exclusion after Blinded Central Adjudication Committee Review*

Reasons for Exclusion	Number of Patients Excluded Following Adjudication	
	CBT n (%) (n= XX adjudicated as ineligible)	Usual Care n (%) (n= XX adjudicated as ineligible)
Fragility fracture (a fall from a standing height or less, that results in a fracture) as their only extremity fracture treated with internal fixation		

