Stress fracture as their only extremity fracture treated with internal fixation		
Patient has a concomitant injury which, in the opinion of the attending surgeon, is likely to impair function for as long as or longer than the patient's extremity fracture(s)		
Patient is facing current or impending incarceration		
Currently not experiencing any pain in the fracture region despite being fully weight bearing		
Patient has active psychosis		
Patient has active suicidality		
Patient has an active substance use disorder that, in the judgement of the treating surgeon, would interfere in the patient's ability to partake in the CBT and/or the study		
Patient does not have the cognitive ability and language skills to participate in CBT		
Patient is already participating in or planning to start other psychological treatments (including CBT) within the duration of the study (12 months)		
Patient does not have consistent online access from a smartphone/internet-enabled device with a minimum operating system able to use the CBT provider's application		
Anticipated problems, in the judgement of study personnel, with the patient participating in CBT intervention and/or returning for follow-up		
Patient is not willing to participate in CBT		
Currently enrolled in a study that does not permit co-enrolment in other trials		
Previously enrolled in the COPE trial		
Patient was not screened/approached within 2-12 weeks following their fracture		
Patient's fracture was not treated operatively with internal fixation		
Patient did not provide informed consent		
Patient is under 18 years of age		
Another reason to exclude the patient (must be approved by the Methods Centre)		

*This table shows all response options for the data collected. In the primary manuscript, some data categories may be removed if there are no responses selected.

Table 3: Baseline characteristics*

	CBT n (%) (n= XX)	Usual Care n (%) (n= XX)
Age in years, mean (SD)		
Sex		
Female		
Male		
Did not want to disclose		
Body mass index in kg/m ²		
Underweight (BMI < 18.5)		
Normal weight (18.5 – 24.9)		
Overweight (25 – 29.9)		
Obese (BMI ≥ 30)		
Did not want to disclose		
Race or ethnicity		
White		
South Asian		
East Asian		
Southeast Asian		
Middle Eastern		
People of African and/or Caribbean Descent		
Indigenous		
Latinx		
Multiethnic Background		
Did not want to disclose		
Latin or Hispanic origin		
Employment prior to injury		
First responder		
Police officer		
Firefighter		
Emergency medical technician		

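### The blanket exclusion of adjudicated-ineligible participants reaches the harms table, so adverse events in randomised people later ruled ineligible would be reported nowhere

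*SAP*

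**What the plan says.** Section 2.1 describes the flow diagram. After the numbers randomly assigned to each group it adds: "It will also include the number of participants who were subsequently deemed ineligible by the Central Adjudication Committee". It then states the rule that "Participants deemed ineligible by the Central Adjudication Committee will not be included in any analysis", citing a paper on post-randomisation exclusions and the intention-to-treat principle.

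The shell headed "Table 2: Reasons for Exclusion after Blinded Central Adjudication Committee Review" has a CBT column and a usual-care column. Its reasons include "Patient has active psychosis" and "Patient has active suicidality". Most of the others have nothing to do with psychiatric risk, for example fragility or stress fracture, no internal fixation, or approach outside the 2 to 12 week window.

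Harms are section 3.4, under the main heading 3.0 (Analysis). The plan is that "The number and percentage of patients experiencing treatment-related serious adverse events and fracture-related complications will be presented by treatment arm", in Table 13, and "No formal statistical testing will be undertaken". Neither section 3.4 nor Table 13 defines a denominator. The one statement of population principle in section 3.1 is limited in scope: "The primary and secondary analyses will be conducted following intention-to-treat (ITT) principles".

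**The concern.** Removing a participant from an efficacy estimate and removing that participant from the harms record are separate decisions. An argument that someone should never have been enrolled may support the first. It does not support the second, because someone who was randomised and began CBT was exposed to it, whatever a committee later decides about eligibility. The SAP makes one decision for both purposes, and the only support it cites is titled as guidance on intention to treat and excluding patients from analysis. It gives no separate reason for extending the exclusion to harms.

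At stake is whether Table 13 is complete. A reader would take it as the full account of treatment-related serious adverse events and fracture-related complications by arm, and nothing else in the report would show what was left out.

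**Working it through.** The SAP states no figure on this point, so there is none to reproduce. The check is a reading of the passages side by side, followed by a formula for the direction of the loss.

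1. **Were the excluded people randomised?** Yes. Section 2.1 calls them subsequently ineligible after counting those assigned to groups, and Table 2 splits them by arm.
2. **Does the rule cover harms?** On its wording, yes. It applies to any analysis, without qualification, and harms sit under the Analysis heading.
3. **Does another statement restore them?** No. The intention-to-treat sentence in section 3.1 names only the primary and secondary analyses. Section 3.4 and Table 13 contain no safety set, exception or footnote.
4. **Are their events shown elsewhere?** No. Figure 1 and Table 2 give numbers of people, and Table 2 gives reasons. No planned table or listing gives their events.

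**Direction and size.** Let f be the share of an arm adjudicated ineligible, r the event risk in those people, and q the risk in the rest. The share of that arm's events that is omitted is

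L = f·r / [f·r + (1 − f)·q].

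The SAP supplies none of f, r or q. Three things follow without them:

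- If r = q, L = f. With an assumed f of 2% to 5%, that is 2% to 5% of events.
- If r > q, L exceeds f.
- If r < q, L is below f. This could happen for treatment-related events if many of those excluded never started CBT.

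**The case against.** The strongest reply is that a descriptive table is not an analysis, so the section 2.1 rule was never meant to reach it. That may be the intention, but the SAP does not say so and its own structure places harms under Analysis. Two programmers could reasonably produce different versions of Table 13.

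A second reply is that the excluded participants are openly accounted for. This stands as far as it goes: their number, arm and reason are reported. Their events are not.

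Three stronger readings are tempting, and the document supports none of them.

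- **Events are removed because they occurred.** A reader might infer that a serious event brings an ineligibility to light and so deletes itself. The SAP does not say whether the committee sees adverse events or whether an event can prompt a review. Table 2 describes the review as blinded, and most of its grounds repeat the screening exclusions of Table 1. This route is neither shown nor ruled out.
- **Participants with suicidality or psychosis drop out of the safety data.** Table 2 lists response options, and its footnote says empty categories may be removed. No such case is known.
- **A large fraction of CBT-arm events would be lost.** Taking f = 2% to 5%, r = 5% to 20% and q = 0.5%, the formula gives 0.001/(0.001 + 0.0049) = 17% at the low end and 0.010/(0.010 + 0.00475) = 68% at the high end. All these inputs are assumptions. They give everyone ruled ineligible a 10- to 40-fold excess risk, although most Table 2 grounds are non-psychiatric. Equal risk gives only 2% to 5%.

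A last objection concerns the remedy and also stands. An unqualified all-randomised harms set would take in people whose Table 2 reason is lack of informed consent, and could count a previously enrolled person twice.

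**Conclusion.** The point holds on the text. A stated rule, applied as written, omits harms in randomised and possibly CBT-exposed participants from the only harms table, and no other output reports them. This goes beyond a detail left to the protocol, because the SAP itself sets a universal rule and makes no exception.

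The size cannot be estimated from the SAP. The loss is proportional to the share excluded if risk is equal, and larger if the excluded are at higher risk. The conclusion assumes that the section 2.1 wording is applied literally and that at least some adjudicated-ineligible participants had recordable events. It does not depend on any event having triggered adjudication, or on any psychiatric case existing. It concerns completeness of harms reporting and does not touch the primary efficacy result.

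**What to change.** - **Section 2.1:** limit the exclusion of adjudicated-ineligible participants to the efficacy analyses.
- **Section 3.4 and Table 13:** define the harms population as all randomised participants by assigned arm, except those whose data may not be used for lack of consent, with any duplicate enrolment counted once.
- **Separate display:** show events in adjudicated-ineligible participants by arm, with the number who started CBT and the follow-up available for them.

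The cost is a sentence or two in each section, a changed denominator and a short extra listing. There are two downsides. The harms denominator will differ from the efficacy denominator and needs a footnote. Percentages in Table 13 may also be diluted if ineligible participants were not followed after adjudication, which the SAP does not address; the separate listing makes that visible.

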Table 12: Sensitivity Analysis of the Impact of CBT versus Usual Care on Primary and Secondary Outcomes Using Available Case Analysis

Outcome	CBT n (%) (n= XX)	Usual Care n (%) (n= XX)	Estimate** (95% CI)	p-value
Primary Outcome				
Moderate to Severe ($\geq 4/10$) PPSP, adjusted mean (95% CI)				
Secondary Outcomes				
SF-36 PCS, mean (95% CI)				
SF-36 MCS, mean (95% CI)				
BPI-SF Average Pain Severity Score, mean (95% CI)				
BPI-SF Pain Interference Score, mean (95% CI)				
Taking an opioid class medication (6 months)				
Taking an opioid class medication (12 months)				

**Estimates are presented as an adjusted risk ratio for the primary outcome, as an odds ratio for the opioid use outcome, and as adjusted mean differences for the remainder of the secondary outcomes.

Table 13: Treatment-Related Serious Adverse Events and Fracture-Related Complications*

Category	CBT n (%) (n= XX)	Usual Care n (%) (n= XX)
Serious adverse event		
Fracture-related complication		
Wound healing problem		
Compartment syndrome		
Superficial infection		
Deep/Organ/Space infection		
Delayed union		
Nonunion		
Malunion		
Implant failure/breakage		
Dislocation/instability		
Heterotopic ossification		
Osteolysis		
Avascular necrosis		
Pain (not otherwise covered)		
Other		

*This table shows all response options for the data collected. In the primary manuscript, some data categories may be collapsed as appropriate or presented in a supplementary appendix.

SUPPLEMENTARY TABLES

Table S1: Open Fracture Characteristics

	CBT n (%) (n= XX open fractures)	Usual Care n (%) (n= XX open fractures)
Gustilo classification I II IIIA IIIB IIIC		
Skin Laceration with edges that approximate Laceration with edges that do not approximate Laceration associated with extensive degloving		
Muscle No appreciable muscle necrosis, some muscle injury with intact muscle function Loss of muscle but the muscle remains functional, some localized necrosis in the zone of injury that requires excision, intact muscle-tendon unit Dead muscle, loss of muscle function, partial or complete compartment excision, complete disruption of a muscle-tendon unit, muscle defect does not reapproximate		
Arterial No major vessel disruption Vessel injury without distal ischemia Vessel injury with distal ischemia		

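### The serious adverse event row of Table 13 is limited to treatment-related events yet shown against a no-CBT arm, so that row is not an interpretable between-arm description

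*SAP*

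**What the plan says.** Section 3.4 is short. It plans a count and percentage of patients and states that "treatment-related serious adverse events and fracture-related complications will be presented by treatment arm". It adds: "No formal statistical testing will be undertaken".

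The table shell it points to is headed "Table 13: Treatment-Related Serious Adverse Events and Fracture-Related Complications" and has two result columns, CBT and usual care, each as a count and percentage. Its first row is labelled "Serious adverse event", without the qualifier in the heading. Below it come a row for fracture-related complications and 14 categories of these, for example "Deep/Organ/Space infection". A footnote says: "This table shows all response options for the data collected".

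The SAP plans no count of serious adverse events of any cause. It does not say what an event must be related to in order to count, or how the restriction applies to a participant in usual care.

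**The concern.** Listing the events attributed to an intervention is a reasonable description of the group that received it. Setting that list beside a group that did not receive the intervention is another matter. A usual-care participant has no CBT to which an event could be attributed. The usual-care percentage is then fixed near zero by the definition of the count and carries no information about how often serious events occurred in that arm.

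What is at stake is the only display of serious adverse events as such. This is a trial of a psychological intervention. A serious event that is not a fracture complication, such as a psychiatric admission, has no other row in Table 13. If nobody attributes it to CBT, the table as titled shows it in neither arm. Readers will compare two adjacent percentage columns whether or not a p-value is printed.

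**Working it through.** The SAP states no serious-event rate and no figure for harms, so there is nothing to reproduce. The check sets the relevant places side by side and then works through what the row would display.

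**Step 1: what 'treatment' refers to.**
- Sections 3.1.1 and 3.1.2 name the exposure in the models as CBT treatment status.
- Table 9 labels the contrast as CBT against no CBT.
- Table 1 lists current or planned psychological treatment, CBT included, as a reason for exclusion, so usual-care participants are not expected to receive CBT from elsewhere.
- Section 3.4 and Table 13 give harms of the fracture their own label, separate from treatment-related events.

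Together these make 'related to CBT' the natural reading. The SAP does not state it.

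**Step 2: what the row displays.** For each arm let *p* be the proportion of participants with at least one serious adverse event of any cause. Let *s* be the share of those participants with at least one event judged treatment-related. The percentage displayed is *s × p*, so

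- displayed difference = *s*(CBT) × *p*(CBT) − *s*(UC) × *p*(UC);
- true difference = *p*(CBT) − *p*(UC).

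If relatedness means relatedness to CBT, *s*(UC) is about 0, and

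- displayed difference ≈ *s*(CBT) × *p*(CBT).

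The usual-care risk *p*(UC) has dropped out. The displayed difference cannot fall below zero, so it can never show fewer serious events under CBT. It is also positive when the true risks are equal, as long as any CBT-arm event is judged related.

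**Step 3: the other reading.** If 'treatment' also covers fracture surgery or usual care, *s*(UC) need not be near zero. The displayed difference equals a constant multiple of the true one only if *s* is the same in both arms. Events in the CBT arm could be attributed to CBT or to the other care, those in usual care only to the other care, and the SAP does not say which attributions count.

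**Step 4: title against row.** Section 3.4 and the title say treatment-related; the row label does not. A row is normally read under its table's title, so this is mainly a labelling fault. Even so, whoever programs the table could fill the row with all events or with related events only and point to wording in support.

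**Step 5: the rest of the table.** No relatedness-to-CBT condition is stated for the 14 complication categories. They are counted in both arms on the same terms, and Steps 2 and 3 do not apply to them.

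**The case against.** The strongest reply has four parts.

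*The plan is descriptive.* It presents events by arm, rules out formal testing and claims no safety inference. This is correct, and it limits the consequences. It does not make the usual-care cell informative.

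*'Treatment' is not defined.* All participants had operative fixation, the SAP calls both arms treatment groups, and definitions of serious events and relatedness are commonly left to the protocol, which was not available for this check. This stands as a limit: a near-zero usual-care count is an inference from the SAP's usage, not something it states. A figure in Section 3.4 was also not available. Step 3 shows that the broader reading leaves the row unclear too.

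*Table 13 does describe safety by arm.* A reader might infer that the whole table cannot show a safety difference. The document does not support that. The complication rows are unfiltered, some of those events could be serious, and they can differ between arms.

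*All-cause events may not exist in the database.* The footnote on response options may mean that only related events were collected, and nothing in the SAP shows that all-cause events were recorded. This stands, and the fix allows for it.

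A reader might also infer that relatedness is judged by someone who knows the arm. The SAP does not say who judges it or whether they are blinded, so this point makes no such claim.

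**Conclusion.** The point holds for the serious adverse event row alone. Followed as written, and with 'treatment' read as CBT, the plan produces a row whose usual-care cell is near empty by construction and whose between-column gap is not a randomised contrast. The mismatch between row label and title adds a minor ambiguity.

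The conclusion rests on one assumption, that treatment-related means related to CBT. The SAP's usage supports it well but does not state it. No numerical size is offered: any percentages would have to assume both the event risks and the empty usual-care cell, and so would only restate the argument. The practical reach is one row of one descriptive table. The primary and secondary analyses and the complication rows are unaffected.

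**What to change.** Which of two versions applies depends on what was collected.

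- **If serious adverse events of any cause were collected:** have Section 3.4 and Table 13 report, by arm, the number and percentage of participants with at least one such event regardless of cause. Beneath it add a sub-row for events judged related to CBT, filled for the CBT arm only and marked not applicable for usual care.
- **If only treatment-related events were collected:** show that row for the CBT arm alone, and state in Section 3.4 and in a table note that it is not a comparison with usual care.

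In either case, use the same term in Section 3.4, the table title and the row label, and say that 'related' means related to CBT if that is what is intended. The complication rows can stay as they are.

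The cost is a few lines of SAP wording and at most one more table row. The downside of the first version is that its count will include events that have nothing to do with CBT.
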